#### 270 **5.3.5. Treatment groups:**

271 **Group A:** (i) 7-week subcutaneous liraglutide treatment once daily, (ii) a 4-week wash-out period,  
272 and (iii) 7-week subcutaneous placebo once daily.

273 **Group B:** (i) 7-week subcutaneous placebo once daily, (ii) a 4-week wash-out period, and (iii) 7-  
274 week subcutaneous liraglutide treatment once daily.

275

276 **5.3.6. Titration schedule:** in order to minimize the loss of weight associated with incretin therapies and to  
277 achieve the optimal dose of liraglutide, active treatment will start at 0.6 mg once daily during the first  
278 week, 1.2 mg once daily during the second week, and 5 weeks at 1.8 mg once daily. Whether a dose of  
279 liraglutide is not well tolerated, it will be reduced to the minimum tolerated dose. Placebo arm will perform  
280 the same scalation that active treated patients.

281

282 **5.3.7. Treatment formulation:** both liraglutide and placebo will be administered subcutaneous using a 3  
283 mL pre-filled pen injector. Regarding liraglutide, one ml of solution will contain 6 mg of the product, so one  
284 pre-filled pen injector will contain 18 mg of liraglutide in 3 mL.

285

[figure not shown]
286 **5.3.8. Sample size:** we have estimated that a number of 76 screened patients at the end of the study will  
287 be able to demonstrate our hypothesis (see below *sample size calculation*).

288  
289 **5.3.9. Baseline treatment:** all type 2 diabetic patients who gave their written informed consent will  
290 continue with metformine ( $\pm$  sulfonyleurea) at the same doses.

291  
292 **5.3.10. Chronogram:** see next page

293  
294 **5.3.11. Visit schedule:** see next page

295  
296  
297  
298  
299  
300  
301  
302  
303

304  
305  
306  
307

	Screening	Basal	Week 2	Week 7	Week 11	Week 13	Week 18
Visit number	-1	0	1	2	3	4	5
Informed Consent	X	-	-	-	-	-	-
Inclusion/exclusion criteria	X	X	X	X	X	X	X
Randomization	-	X	-	-	-	-	-
Physical examination	X	X	X	X	X	X	X
Liraglutide/placebo dispensed	-	X	X	-	X	X	-
Drug accountability	-	-	X	X	-	X	X
Concomitant Medication	-	X	X	X	X	X	X
Expiratory flows	-	X	-	X	X	-	X
Pulmonary volumes	-	X	-	X	X	-	X
6-minute walking test	-	X	-	X	X	-	X
Respiratory polygraphy	-	X	-	X	X	-	X
Nocturnal Oxygen Saturation	-	X	-	X	X	-	X
Serum Surfactant A Protein	-	X	X	X	X	X	X
Inflamm. markers in exhaled air	-	X	X	X	X	X	X
Laboratory	-	X	X	X	X	X	X
Urine pregnancy test (if applicable)	X	-	-	-	X	-	-

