## 387 **8. SAMPLE SIZE CALCULATION**

388

389 The inclusion of 50 patients will achieve a 80% of statistical power ( $\beta=0.2$ ) to detect a significant increase,  
390 due to the treatment, in the FEV1 levels of at least 20%, assuming a baseline expected values of FEV1  
391 for untreated patients of  $88.4 \pm 19.7$  [as previously reported by Lecube et al (Diabetologia 2010)] and using  
392 and ANOVA test to specifically assess the effect in a cross-over design, setting the threshold for statistical  
393 significance at 5% ( $\alpha=0.05$ , one sided). For this computation, the within mean square error of the ANOVA  
394 test for repeated measurements was calculated as  $\sqrt{2 \times (19.7^2)} = 27.86$ . Sample size will be increased in  
395 10 patients according to an expected drop-out rate of 20%. Hence, a total of 60 patients will be included  
396 in the cross-over randomized trial. In addition, in order to avoid unexpected changes in the final sample  
397 size, we will recruit only patients with a baseline decrease in FEV1 equal or higher than 10% in the  
398 percentage predicted value.

399 However, data regarding factors to be analysed in the present project (for example, levels of  
400 serum surfactant A protein and parameters measured in the exhaled air) are lacking and, therefore, to  
401 give ourselves a safety margin we have increased the sample size. Hence, we hope that the number of  
402 76 patients will be sufficient to demonstrate our hypothesis.

403

404

405 **9. STATISTICAL ANALYSIS**

406

407 First, a homogeneity analysis will be undergone to compare patients in both groups (A and B) with  
408 regards to basal clinical and anthropometric variables. Mean (and standard deviation) and frequency (and  
409 percentage) will be used to describe quantitative and qualitative variables respectively, using Mann-  
410 Whitney test for categorical variables to assess the differences between groups. Second, the effect of the  
411 treatment will be evaluated using an ANOVA test with repeated measures, also adjusting for the potential  
412 carry-over effect and those potential confounders detected in the homogeneity analysis, using for this  
413 purposed mixed linear models. Third, similar analysis will be performed to assess the effect of the  
414 treatment on the secondary outcomes. All analysis will be obtained using R statistical package and  
415 threshold for statistical significance will be set at 0.05.

416

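### Section 9 adjusts the primary FEV1 effect for carry-over in a two-period crossover, without stating the coding or a period term; the usual coding discards the within-patient comparison

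*Combined protocol and SAP*

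**What the plan says.** Section 9 states that the effect of "treatment will be evaluated using an ANOVA test with repeated measures, also adjusting for the potential" "carry-over effect and those potential confounders detected in the homogeneity analysis", by means of "purposed mixed linear models". It then applies a similar analysis to the secondary outcomes, and the "threshold for statistical significance will be set at 0.05" without stating one- or two-sided. It does not say how carry-over is coded, whether period or sequence is in the model, which random effects are used or which visits enter.

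Section 5.3.5 sets out two sequences. Group A receives ("i) 7-week subcutaneous liraglutide treatment once daily, (ii) a 4-week wash-out period" and then placebo; Group B receives the reverse. The visit schedule in Section 5.3.11 places "Expiratory flows" at baseline and weeks 7, 11 and 18. FEV1 is the primary measure (Section 7.1). Section 8 sizes the trial on a crossover ANOVA and makes no allowance for a carry-over term.

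**The concern.** A crossover is chosen so that each patient serves as his or her own control. In a two-by-two crossover there are only four cell means, so an ordinary carry-over term added to treatment and period leaves no information for a within-patient treatment estimate. A reader who follows Section 9 in the usual way would analyse the primary outcome as a parallel-group comparison of the first period.

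Other readings of the same sentence give other estimates. Some keep the within-patient comparison; one lets a period effect (test learning or season, for example) into the treatment effect. Because the plan does not choose, the analyst could do so after seeing the data.

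A smaller point is that covariates are to be picked by testing baseline differences between randomised sequences, which makes the model data-driven.

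**Working it through.** **Inputs from the plan.** Section 8: 50 patients, SD 19.7, untreated mean 88.4, a 20% effect, one-sided 5%. Section 5.3.4: 1:1 allocation, hence 25 per sequence. The plan gives no within-patient correlation ρ; 0, 0.5, 0.8 and 0.9 are assumed, with the same correlation between all visits.

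**The plan's own figure.** Section 8's 50 is reproduced by treating 27.86 as the SD in a two-sample comparison and 20% as 20 points: 2 × (1.645 + 0.842)² × 27.86² / 20² = 24 per sequence, 48 in all (50 with the t distribution). If 20% means 17.68 points (20% of 88.4), the same formula gives 31 per sequence, or 62. The value 27.86 = √(2 × 19.7²) corresponds to ρ = 0, so Section 8 takes no credit for within-patient correlation.

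**What each model estimates.** Let τ be the treatment effect, π the period-2 effect and λ the carry-over of liraglutide into period 2. The cell means are

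- A1 = μ + τ
- A2 = μ + π + λ
- B1 = μ
- B2 = μ + π + τ

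1. *Treatment + period + carry-over.* Four means and four unknowns give one solution, τ = A1 − B1. Weights on (A1, A2, B1, B2) are (1, 0, −1, 0). SE = 19.7 × √(2/25) = 5.57 whatever ρ is.
2. *Treatment + period, with or without sequence, no carry-over.* Weights are (½, −½, −½, ½). SE = 19.7 × √((1 − ρ)/25).
3. *Treatment + 0/1 carry-over, no period.* λ absorbs A2. Weights are ((1 − ρ)/2, 0, −1, (1 + ρ)/2), so a share (1 + ρ)/2 of any period effect enters the treatment estimate.
4. *All four visits, with visit, treatment and one common carry-over at weeks 11 and 18.* Within-patient information is partly kept.

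| | ρ = 0 | 0.5 | 0.8 | 0.9 |
|---|---|---|---|---|
| SE, model 1 | 5.57 | 5.57 | 5.57 | 5.57 |
| SE, model 2 | 3.94 | 2.79 | 1.76 | 1.25 |
| Variance ratio, 2/(1 − ρ) | 2 | 4 | 10 | 20 |
| 95% CI half-width, model 1 | 11.2 | 11.2 | 11.2 | 11.2 |
| 95% CI half-width, model 2 | 7.9 | 5.6 | 3.5 | 2.5 |
| Detectable at 80%, one-sided, model 1 | 14.1 | 14.1 | 14.1 | 14.1 |
| Detectable at 80%, one-sided, model 2 | 9.9 | 7.0 | 4.4 | 3.1 |
| Period effect entering, model 3 | 50% | 75% | 90% | 95% |
| SE, model 4 | 4.55 | 3.65 | 2.43 | 1.74 |

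**Power under model 1 (t, 48 df).** For 17.68 points: 93% one-sided, 87.5% two-sided. For 20 points: 97% and 94%. For 8.84 points (half the planned effect, illustrative): 47% one-sided, against 93% under model 2 at ρ = 0.5.

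**Check by simulation.** 150 trials were fitted by REML with ρ = 0.8, a true effect of 17.68 and a period effect of 5. Model 1 equalled the period-1 mean difference to 1e-12, with mean SE 5.51. Model 2 with sequence gave 17.45, mean SE 1.75. Model 3 gave 22.05: (22.05 − 17.68)/5 = 87% of the period effect.

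**Covariate selection.** With complete data, adding a patient-level covariate changed the model 2 estimate by less than 1e-12. It does move model 1. An imbalance just reaching p = 0.05 is 2.011 × √(2/25) = 0.569 SD. With a covariate correlated 0.3 to 0.5 with FEV1 (assumed), the shift is 0.569 × 19.7 × 0.3 to 0.5 = 3.4 to 5.6 points.

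**The case against.** The strongest reply is that the collapse depends on a coding the plan never states. That is true. If carry-over is represented by a sequence term, nothing is lost. If patients are fixed blocks, carry-over is aliased with treatment and period, and software that drops it returns the within-patient estimate. The period leak is likewise specific to 0/1 coding: plus/minus coding without period gives the period-1 contrast instead. This limits the claim to the usual coding, but it also shows how far the answer depends on an unstated choice.

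A second reply is that week-0 and week-11 FEV1 would recover precision. They do so partly. With separate carry-over terms at weeks 11 and 18 the SE is 5.57 / 4.83 / 3.34 / 2.43 at the four correlations, but the estimate is still a period-1 contrast, now baseline-adjusted, and Section 9 does not say these visits are used.

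A third is that the absolute figures may be too large. Section 1.5 expects 60 patients at the end and 76 included; the model 1 SE would be 5.09 at 60 and 4.52 if all 76 had a week-7 value. Requiring FEV1 at least 10% below predicted may also cut the SD. If that truncates a normal distribution at 90% of predicted (an assumption), the baseline SD falls to about 12.2, and at an untruncated correlation of 0.8 the variance ratio is about 6 rather than 10. These points stand as qualifications. A different N does not change the ratios for the same patients, and the direction is the same throughout.

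Finally, dropping the term trades variance for possible bias, and the documents do not show that four weeks of wash-out is enough for FEV1. That cost is real and is stated with the fix. The covariate point is minor, and with complete data it has no effect once the within-patient model is used.

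**Conclusion.** The concern holds. Section 9 commits the primary analysis to a carry-over adjustment whose usual form, on end-of-period values, reduces the crossover to its first period. On Section 8's N and SD, variance rises by a factor of 2/(1 − ρ): 2 at zero correlation and 4 to 20 for assumed correlations of 0.5 to 0.9. The trial does not become underpowered for its planned 20% effect. The harm is a wider interval, low power for smaller effects, possible period bias if period is left out, and an analysis choice left open until the data are seen. The omission in the text is certain; the size depends on the coding, the visits used, the unstated correlation and the SD in the restricted population.

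**What to change.** State the primary model in Section 9: a linear mixed model of week-7 and week-18 FEV1 with treatment, period and sequence as fixed effects, a random patient effect and no carry-over term.

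Describe carry-over separately as the week-0 to week-11 change in FEV1 by sequence, with a confidence interval, and do not let it select the primary model. Keep a carry-over model only as a sensitivity analysis with its coding written out, for example visit (weeks 0, 7, 11, 18), treatment, one common after-liraglutide effect at weeks 11 and 18, and a random patient effect.

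Remove the selection of confounders from the homogeneity analysis, report baseline descriptively, and name any covariates in advance.

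This needs no new visit, measurement or patient. The cost is exposure to bias: without the term the estimate has expectation τ − λ/2, so half of any carry-over still present at week 18 (in Group A, 11 weeks after the liraglutide period ends) remains, pulling toward no effect if benefit persists. The week-11 check is imprecise at low correlation: the SE of the between-sequence difference in change, 19.7 × √(2(1 − ρ)) × √(2/25), is 7.88 / 5.57 / 3.52 / 2.49 at ρ = 0 / 0.5 / 0.8 / 0.9. It should be reported as a description, not as proof that carry-over is absent.

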93 treatment on lung function could be attributed to their action on surfactant production. For this  
94 purpose changes from basal in serum levels of surfactant A protein, the major surfactant-  
95 associated protein, will be evaluated.

96  
97 **d.-** To establish the effect of 5-week liraglutide 1.8 mg once daily treatment compared to placebo  
98 in type 2 diabetic patients on lung inflammation. For this purpose inflammation markers in  
99 exhaled breath concentrate (nitric oxide, pH, and concentration of nitrites, nitrates and  
100 isoprostane) will be measured.

101

102 **1.3. Study design:** This is a double-blind, randomized, crossover, placebo-controlled study, with two  
103 parallel groups (liraglutide once daily sc vs. placebo sc/once daily) of 18-weeks.

104

105 **1.4. Study periods:** (1) selection, (2) active treatment (7 weeks, 5 of them at 1.8 mg once daily), (3)  
106 wash-out (4 weeks), and (4) alternative treatment (7 weeks).

107

108 **1.5. Sample size:** We have estimated that a number of 60 patients at the end of the study will be  
109 sufficient to test our hypothesis. However, taking into account a drop-out ratio of 20%, the final number of  
110 patients that will be included in the study will be 76 (see details in point 9)

111

112 **1.6. Population to be examined:** Type 2 diabetic patients, treated with metformin ( $\pm$  sulfonylurea) at a  
113 stable dose for at least the previous 3 months, with haemoglobin A1c between 7.0 and 10.0%, BMI  $\geq$  30  
114 Kg/m^2, and no known lung disease.

115

116 **1.7. Participating institutions:** 5 reference Spanish hospitals.

117

118

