### 242 **5.3 Study design**

243

244 **5.3.1. Study type:** This is a phase IV double-blind, randomized, crossover, placebo-controlled study, with  
245 two parallel groups (1.8 mg of liraglutide once daily sc vs placebo once daily sc) for 14 weeks.

246

247 **5.3.2. The consent process:** The consent process will begin when a potential research patient is initially  
248 contacted. Prior to any study-related activity, including screening procedures, potential candidates to be  
249 recruited will receive extensive, both oral and written, information about the study, including the risk

250 associated with the study procedures and study-drug. In addition to signing the consent, the patient will  
251 enter the date of the signature on the consent document, to permit verification that consent was actually  
252 obtained before the patient began participation in the study. A copy of the consent document will be  
253 provided to the patient and the original signed consent document will be retained in the study records.

254

255 **5.3.3. Screening phase (population to be examined):** The study will include type 2 diabetic patients,  
256 treated with metformin ( $\pm$  sulfonylurea) at a stable dose for at least the previous 3 months, with HbA1c  
257 between 7.0 and 10.0%, BMI  $\geq$  30 Kg/m^2, and no known lung disease. The patients included in the study  
258 will be recruited from the Endocrinology Departments of all the participating centers and will be followed-  
259 up by the endocrinologists and pneumologists in the investigating teams. The main exclusion criteria  
260 include type 1 diabetes mellitus, treatment with insulin, dipeptidyl peptidase-4 inhibitors and/or  
261 pioglitazone, history of smoking habit, chronic respiratory disease, asthma, cardiovascular disease,  
262 hearth failure, stroke, and/or chest wall disease.

263

264 **5.3.4. Inclusion phase:** After informed consent, the recruited patients will be transferred to Pneumology  
265 Departments where the following examinations will be performed: expiratory flows, pulmonary volumes, 6-  
266 minute walking test, non-attended respiratory polygraphy with oxygen saturation monitoring, inflammatory  
267 markers in exhaled air, and serum surfactant A protein measurement. After these evaluations patients will  
268 be randomly allocated in a 1:1 ratio to one of the two treatment groups.

269

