### 312 **6.1. Inclusion criteria:**

- 313 - Type 2 diabetic patients ( $\geq 18$  years of age) with more than 5 years of evolution of the disease,
- 314 - treatment with **metformin** ( $\pm$  sulfonylurea) at a stable dose for at least the previous 3 months,
- 315 - HbA1c  $\geq 7.0$  and  $\leq 10.0\%$ ,
- 316 - body mass index  $\geq 30$  Kg/m^2,
- 317 - no known lung disease,
- 318 - baseline reduction in FEV1 equal or higher than 10% in the percentage predicted value,
- 319 - provision of an informed consent form signed and personally dated by the patient.

320

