### 380 **7.3. Other variables to be evaluated:**

- 381 - Anthropometric data: weight, height, waist circumference, and neck circumference
- 382 - Daytime sleepiness through the *Epworth Sleepiness Test*
- 383 - Fasting blood glucose, HbA1c, fructosamine, fasting insulin, and insulin resistance measured by
- 384 HOMA-IR.

385

386

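### Section 9 picks covariates for the primary FEV1 model by comparing the randomised sequences at baseline, so the model is not fixed in advance; week-0 FEV1 should be prespecified, though it gains precision only under some codings of carry-over

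*Combined protocol and SAP*

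**What the plan says.** Section 9 begins with a comparison of the two arms: "a homogeneity analysis will be undergone to compare patients in both groups (A and B) with" regard to baseline clinical and anthropometric variables. Treatment is then assessed by repeated-measures ANOVA, adjusted for the potential "carry-over effect and those potential confounders detected in the homogeneity analysis, using for this" purpose mixed linear models. Secondary outcomes follow the same route: "similar analysis will be performed to assess the effect of the" treatment on them.

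Groups A and B are the two treatment sequences. Section 5.3.4 has patients "be randomly allocated in a 1:1 ratio to one of the two treatment groups" after the baseline examinations, which include expiratory flows. In the Section 5.3.11 visit schedule the row "Expiratory flows" is marked at baseline and at weeks 7, 11 and 18.

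Section 9 does not list the variables screened, define what counts as detected, give week-0 FEV1 a role, code the carry-over adjustment, mention a period term or name the response visits. No other section fills these gaps. The one screening test named, Mann-Whitney, is described as being for categorical variables. A general threshold of 0.05 is given.

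**The concern.** Allocation is random, so among all randomised patients a baseline difference between A and B is a chance difference. Testing for it says nothing about which covariates predict FEV1, yet the result decides what enters the primary model. That model cannot be written down before the data are seen.

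The obvious candidate covariate is the week-0 value of the primary endpoint. It is collected anyway, but under this rule it would be used only after an unlucky draw. If treatment is estimated between patients, leaving it out costs precision.

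**Working it through.** **The plan's own figure.** Section 8's √(2 × 19.7²) = 27.86 reproduces. Its 50 patients follow from a two-group t calculation with SD 27.86 and one-sided 0.05 if the 20% is read as 20 points: 25 per group, power 0.804. Read as 20% of 88.4 = 17.7 points, the same calculation gives 64. The sample size is not disputed here, and the smaller target is used below.

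**Inputs.** Mean 88.4 and SD 19.7 are from Section 8. Sixty completers, 30 per sequence, are from Section 1.5 ("We have estimated that a number of 60 patients at the end of the study will be" sufficient); Section 8 counts 50 before drop-out. The baseline–outcome correlation r is not in the documents; 0.5, 0.7, 0.8 and 0.9 are assumed. Section 6.1 requires a "baseline reduction in FEV1 equal or higher than 10% in the percentage predicted value". Read as FEV1 at or below 90% predicted, this truncates baseline; results are given both ways.

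**Step 1. How often week-0 FEV1 enters.** Under randomisation a 0.05 rule flags it in about 5% of trials. Simulated Mann-Whitney tests gave 5.0%, 4.8% and 4.6% at N = 50, 60 and 76.

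**Step 2. First-order carry-over plus period, weeks 7 and 18 as responses.** The expected means are:

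| Sequence | Week 7 | Week 18 |
|---|---|---|
| A (liraglutide first) | π₁ + τ | π₂ + λ |
| B (placebo first) | π₁ | π₂ + τ |

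Four means and four parameters, so the estimate of τ is the week-7 difference between A and B. A simulated mixed model confirmed it (0.810 both ways). Then:

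- without week-0 FEV1: SE = 19.7 × √(2/30) = 5.09
- with it: SE = 5.09 × √(1 − r²)

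| r | 0.5 | 0.7 | 0.8 | 0.9 |
|---|---|---|---|---|
| Without, no truncation | 5.09 | 5.09 | 5.09 | 5.09 |
| Without, truncated at 90 | 4.67 | 4.24 | 3.96 | 3.60 |
| With | 4.41 | 3.63 | 3.05 | 2.22 |

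**Step 3. Treatment, period and sequence.** Let d be a patient's week-7 minus week-18 value. With complete data the treatment estimate is half the difference in mean d between A and B. A baseline covariate contributes equally to both weeks and cancels from d. With within-patient correlation set to r, SE = 19.7 × √((1 − r)/30) = 2.54/1.97/1.61/1.14, with or without the covariate. In a simulated trial the estimate was −1.365 both ways.

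**Step 4. Other codings (r = 0.8, no truncation).** Carry-over without period: SE 2.22, or 2.11 with baseline. If all four spirometry visits are responses, week-0 FEV1 is already used implicitly: SE 2.21 with one carry-over term, 3.05 with separate week-11 and week-18 terms.

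**Step 5. Error rate and power under Step 2.** Simulation, two-sided 0.05: screen week-0 FEV1 with a t test at 0.05 and adjust only if it is flagged; compare with always adjusting. Results are for r = 0.5/0.7/0.8/0.9 and 60 completers.

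- Type I error of test-then-adjust: 4.7/4.3/3.9/3.2% truncated; about 4.5/4.0/3.4/2.4% untruncated.
- Power at a fixed 17.7 points, test-then-adjust: 93.5/94.1/94.5/94.7% untruncated; 96.3% or more truncated. Always adjusting: 97.5% or more.
- Truncation lowers the baseline mean to about 73.7, so a relative 20% is 0.20 × 73.7 = 14.7 points. Test-then-adjust power is then about 88/93/96/99% (81/88/93/97% with 50 completers).
- Illustration only, 8.84 points (10% of 88.4, not the protocol's target), untruncated: 40/41/41/42% against 50/66/81/97%. Truncated: 46/54/61/70% against 50/66/81/97%.

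**The case against.** The strongest reply is that in a conventional crossover model the issue has no numerical effect. By Step 3, with complete data no patient-level baseline covariate moves the treatment estimate, so a chance-selected one does no harm and a prespecified FEV1 does no good. This stands: under that coding only the prespecification point is left. But Section 9 asks for carry-over adjustment without coding it, so the costly reading is open.

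Several stronger conclusions are tempting and are not supported.

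- **Inflated false positives.** A reader might infer this from data-driven adjustment. With one screened covariate the rule was conservative. Selection among several covariates was not assessed, so neither inflation nor its absence is shown for that case.
- **An underpowered trial.** Power for the planned effect is high under either rule. The visible loss is at smaller effects, under the Step 2 coding, and depends on r.
- **Firm flag rates.** The 5% figure requires reading detected as p<0.05 and extending Mann-Whitney to quantitative variables; read literally, Section 9 names no test for FEV1. A reader might also take the ten variables of Section 7.3, beginning with "Anthropometric data: weight, height, waist circumference, and neck circumference", and compute 1 − 0.95¹⁰ = 40% for at least one chance flag. That section is not the screening list, and its variables are not independent (HOMA-IR is derived).
- **Carry-over must leave the primary model.** Its coding changes precision more than week-0 FEV1 does, but dropping it reverses an explicit choice in Section 9 and is a separate question.

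One qualification also stands. Sections 5.2 and 6.3 remove some patients during the trial and Section 9 names no analysis set. Among completers, imbalance need not be pure chance. That is no reason to let a balance test choose the covariates.

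**Conclusion.** The point holds as one of prespecification under every coding of carry-over, and for the primary and secondary outcomes alike.

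The precision loss is conditional. With first-order carry-over plus period and weeks 7 and 18 as responses, omitting week-0 FEV1 multiplies the standard error by 1/√(1 − r²) without truncation: 5.09/4.41 = 1.15 at r = 0.5 and 5.09/2.22 = 2.29 at r = 0.9. It is less if baseline is truncated at 90% predicted. In a complete-data treatment, period and sequence model the loss is nil. These figures rest on 60 completers, SD 19.7 and an assumed r.

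This is worth correcting because it is almost free. It does not threaten the trial's validity or its power for the planned effect.

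**What to change.** In Section 9:

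1. Delete the clause that adds confounders found by the homogeneity comparison. Describe baseline by sequence, without using tests to choose covariates.
2. Prespecify week-0 FEV1 as a covariate in the primary model, and each secondary outcome's own week-0 value in its model.
3. State how carry-over is coded, whether a period term is included, and which visits are responses. If week-0 FEV1 is itself a response, say so, since it is then already in the model. Decide separately whether carry-over stays in the primary model.

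The cost is wording and one degree of freedom, with no new data. In a treatment, period and sequence model the covariate adds nothing with complete data and little with drop-out: with 76 randomised, 16 of them contributing period 1 only, the standard error goes from 1.59 to 1.56 at r = 0.8. It does no harm there, and it protects precision if first-order carry-over is retained.
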